Title: Virtual Neuroprosthesis: Restoring a Sense of Touch to Amputees

Clinical Trials number: NCT03581448

Protocol and Statistical Analysis

August 18, 2021

SCH: INT: Virtual Neuroprosthesis: Restoring Autonomy to People Suffering from Neurotrauma

1. Project Summary: The goal of this project is to quantify motor task performance (tasks reminiscent of everyday life such as object transportation, arm motion and reaching) in normal subjects, amputees and limb-absent people controlling a robotic arm and hand. Participants are subjected to a virtual loss and recovery of their tactile experience via modulation of a noninvasive haptic feedback system attached to their body, to mimic the experience of neural plasticity that occurs during peripheral nerve regeneration. We hypothesize that trials during which subjects are provided with more accurate, less noisy haptic feedback will lead to stronger and more timely somatosensory activity as measured with EEG neuromarkers, which in turn, will lead to better behavioral performance while using the artificial hand. This research plan is minimally intrusive to people and poses only minimal risks commonly encountered in daily activities.

2. Objectives: Our specific aim is to determine the optimum conditions that promote sensory restoration in limb-absent people, with the development of adaptive haptic feedback laws and protocols that mimics the experience of neural plasticity.

3. Background & Rationale: Toward developing haptic-smart limb prosthesis: One significant challenge for people who use prosthetic hands is the inability to directly feel anything that is grasped by the prosthesis (grant proposal sections 1.2-3 for detailed rationale and references). An invasive method at the cutting edge to reconnect limb-absent subjects' sense of touch is through direct neural feedback with an implanted electrical stimulator in the nervous system (grant proposal section 1.5). This has been helpful to reconnect a severed sense of touch with sensors on their prosthetic hands (grant proposal section 1). But the self-organizing process of peripheral nerve pathway restoration, which is well studied at the physiological level *in vivo*, is complex and more poorly understood at the functional level (grant proposal sections 1.4, 2.3, 2.5). To develop restoration of haptic sensation in users of prosthetic hands, two important questions need more research: how does the functional process of sensory restoration occur in people with damaged peripheral nerves undergoing regeneration? And to what extend does somatosensory restoration depend on the action of the person and its corollary pattern of afferent action potentials? Answers to those questions are progressing slowly with invasive studies, due to restrictions placed on safety and ethics while experimenting with electrode implantation and nerve stimulation *in vivo*. Our proposed virtual neuroprosthesis circumvents those limitations by setting a surrogate regenerating nerve *in vitro*. Rats' peripheral neurons are cultured in microfluidic chambers and then subjected to trauma. By participating in experiments in which they control robotic arms and hands, subjects contribute to the regeneration of the traumatized neurons *in vitro*: the haptic experience that their actions causes is sensed by the robotic hand and transformed into biologically-realistic trains of action potentials, which are conveyed to the cultured nerves to stimulate nerve regrowth electrotactically. In return, impedimetric and microscopic assessments of nerve regeneration are used to modulate the quality of an indirect haptic feedback received by the subject (a pressure-varying cuff actuator applied to a proximal limb site), so that interaction between action and perception can be studied in humans while *in vitro* neurons regenerate. Subjects are never in direct contact with the nerve culture in any way (the state of cultured nerve regeneration just becomes a control parameter to modulate how clearly haptic feedback is provided to the subject, with poorly regenerating nerves giving rise to poor haptic feedback and vice versa), and the haptic stimulation is entirely noninvasive, making this experimental program one with minimal risks. From the viewpoint of the subject, the experiment just looks like a psychophysics study during which tactile information is varyingly facilitated or impeded during task performance.

4. Research Plan:

(a) Study Design and Timeframe of the Study

The study follows an experimental research plan under consideration for an award at NIH and its performance is planned for a duration of 4 years. All experiments are conducted on the Boca Raton Campus of Florida Atlantic University. The study includes a fractional factorial experimental design with repeated measurements.

(b) Research Methods

Over one or multiple days, we examine neurobehavioral processes in people controlling a robotic arm and hand to perform simple motor tasks (e.g. fragile object transportation), while a virtual peripheral nerve regeneration protocol provides users

with biologically-realistic, idiosyncratic parameters for the restoration of haptic sensation (in double-blind fashion, the cellular neurophysiologists characterizing neural regeneration with microscopy are unaware of subjects' name and condition; and the human-subject experimenters are unaware of the haptic feedback parameter that will be used in the experiment each day, which is entered by the neurophysiologist in a black-box section of the software in the case of microscopic evaluation of nerve regeneration (early part of the project), or which is automatically input by the system in the case of real time impedimentic measurements (later part of the project)). The main experimental factors are 'haptic feedback', with three modalities: full, partial (nerve-regeneration dependent) and null; and to challenge human control strategy and impose demand on haptic information, the 'transported object weight' (heavy, medium and lightweight).

Recording techniques: Subjects' electroencephalography (EEG), electromyography (EMG) and behavioral performance scores (number of drop and breakage, speed) are recorded, as well as subjective self-report (perceived task difficulty).

Other significant materials: Subjects are equipped with a soft haptic feedback armband, a cuff with variable inflation that informs of the pressure measured within the robotic hand as it manipulates objects. Subjects face a computer display (initial training session) or the robotic arm and hand (subsequent sessions).

Procedures: After explanation of the experimental goal and signature of a written informed consent, subjects are prepared for EEG recording, an EMG array and a soft haptic feedback armband are placed on their missing (or dominant) hand. In a series of trials, they use a robotic arm and hand to perform a fragile object transportation task or various control motor actions. The task parameters are varied between trials (presence and quality of haptic feedback, weight of the visually-identical object). The task, including EEG, EMG and armband preparation, instruction and numerous breaks, and removal of the EEG electrode array, is under 2 hours. No activity is physically strenuous and subjects can ask for a break at any time. While in preliminary phases of this study, we may need to test one of more of these individual subsystems (EEG, EMG, soft actuators) independently with human subjects. Thus on the consent form we have specified this by including boxes to be checked for the combination of EEG, EMG, and soft actuators that will be evaluated during experiments.

Time commitment: Each experiment will last at most 2 hours. Subjects are free to withdraw from the study at any time with no repercussion whatsoever. At the end of each experiment, subjects are offered continued participation over the consecutive days of the week.

(c) Study Population: Subjects are 18-65y.o. volunteer with intact limbs, amputation or congenital limb absence. Inclusion criteria are normal/corrected-to-normal vision, general good health. Exclusion criteria are an amputation wound that has not yet healed, the absence of a suitable length of residual limb for placement of haptic feedback controller and EMG sensors, presence of pain that prevents utilization of those experimental appliances and the use of psychoactive drugs that modifies baseline neural activity.

[name] has demonstrated the ability to recruit amputee subjects and successfully design robotic control experiments for them (grant proposal section 2.1-2 and 3.6). Based on a power analysis of preliminary data of grasp performance metrics with amputees and best estimates (standardized probability of 0.05 and statistical power of 0.8), a minimum of seven subjects will be required for adequately powered behavioral analysis. EEG analysis, on its side, requires a minimum of 12 subjects per group (Picton et al., Psychophysiology, 2000). Therefore, our study aims for 3 x 12 subjects (control, amputees, limb absent) and provides for pilot data collection and expected attrition to a total of 50 subjects. (Past experience has shown amputees and limb-absent people to be dedicated experimental volunteers, therefore at the present time, we factored an attrition rate of 32%).

d) Recruitment Plan: We plan to recruit test subjects by distributing flyers throughout Florida Atlantic University campus which describe the key points of the experiment and lists [name] office phone number and email address. Due to the difficulty in recruiting well-qualified limb-absent subjects, flyers may also be posted on campuses of nearby universities, including Florida International University, Nova, etc.

After volunteers contact the experimenters, we will screen subjects for inclusion/exclusion criteria over the phone and for those included, we will arrange a time to perform the first experiment. Before the experiment, we will explain the study objectives and procedures, answer questions and then we will ask subjects to read and sign the informed consent form.

A participation stipend will be offered to the participants in the studies in the form of prepaid gift cards from Amazon or equivalent, with no penalty if the subject withdraws during the session. We propose to compensate all subjects who participate in this study with \$80 to offset their travel time and expenses.

(e) Analysis Plan: We compare the neural (somatosensory neuromarkers) and behavioral characteristics (performance, subjective report) for each object weight and each feedback modality. We hypothesize that trials provided with less noisy, more accurate tactile feedback will lead to stronger and more timely somatosensory activity as measured with EEG neuromarkers, which in turn, will lead to faster and better behavioral performance while using the artificial hand. EEG analysis is conducted using the methods developed by [name] et al., PNAS, 2007. Nonparametric Mann-Whitney U-tests will be performed on the subjective evaluations and a multifactor ANOVA will be performed on the quantitative success rates related to the number of times the objects were dropped or broken, and the speed of transport. Results will be disseminated as oral and poster presentations at conference, proceedings and journal submissions.

5. Benefits: This study presents minimal risks and offers no direct health benefits to the participating subjects but aims to advance understanding on the behavioral and brain mechanisms underlying somatosensation and its plasticity. Participation in this experiment is important for society. Increased understanding on the plasticity of somatosensation will be broadly useful for behavioral neuroscience. The scientific advances expected to result from this research will specifically benefit amputees and limb-absent people who use prosthetic hands or disabled individuals who rely on robotic assistants. There are others who could benefit from this research as well, for example, doctors who perform robot-assisted surgery and their patients, or people having suffered from neurotrauma.

6. Risks: This study will involve no more risk than encountered during routine medical, psychological examination or during daily life. The EEG employed in this study is a medical grade system with optical isolation that prevents electrical risk. Sensitive EEG equipment is single-use and sterile (syringes, canula, qtips), or when not possible (EEG and EMG electrodes), decontaminated with compliant medical procedures for infectious risk. All personnel participating in this research are trained and certified by [name], who has managed EEG training at the Center for Complex Systems and Brain Sciences since 2004.

Application of EEG and EMG electrodes presents a small risk of skin irritation that is rare and usually disappears within a day or two. Application of the haptic stimulator is calibrated to avoid excess pressure and pain, and subjects are encouraged by instruction to provide continuous feedback on discomfort.

Performance of the robotic control task is designed to minimize strain and fatigue. There are small risks of tension or fatigue in the muscles of the limb used to generate the robotic control signal; of visual fatigue while concentrating on the computer screen or robotic hand; of important demand on attention leading to mental fatigue. Those effects are rare and, based on previous studies, we expect that no adverse consequence persists beyond a few hours. Experimenters are present at the side of the subject at all time, and subjects are free to interrupt a session at any time.

7. Informed Consent Process: After volunteers contact the experimenters by phone or in person, we will ask subjects for verbal consent to conduct the screening for inclusion/exclusion criteria. We will inform subjects that they are free to answer each and all questions from the screening procedure. Upon acceptance, the experimenter will then go through the screening procedure, and for people meeting the inclusion requirements, will arrange a scheduled time to perform the first experiment. Just before the scheduled experiment, we will explain the study objectives and procedures, answer questions and then we will ask subjects to read and sign the informed consent form.

(a) Inclusion/ exclusion screening procedures: Subjects are asked details about their vision (normal/corrected-to-normal; poor; Prefer not to answer [PNTA thereafter]), general good health (yes, no, PNTA), if appropriate amputation type, healing status (yes, no, PNTA), presence of neuropathic pain (yes, no, PNTA), and use of psychoactive drugs (yes, no, PNTA).

(b) Deception: No deception will be used either during the screening process or during the experiment.

(c) Cognitively- or decisionally- impaired subjects: We will not enroll cognitively or decisionally-impaired subjects. Some subjects will have a physical disability (absence or loss of a limb): such does not affect their ability

to understand the purpose and procedure of the experiment, or to make an informed decision to participate and provide informed consent.

(d) **Emancipated minors:** We will not enroll emancipated minors.

(e) **Non-English speaking subjects:** We will not enroll non-english speaking subjects.

8. Informed consent document: Human subjects will be informed of the study objectives and procedures before being proposed to consent to participate. We will indicate that participation is on a voluntary basis and we will use a written informed consent, approved by FAU IRB and current, to document voluntary participation.

9. Research Materials, Records, and Privacy:

(a) **type of information collected:** We will collect demographic information as required by NIH enrollment report if consented by the subject (subjects are able to decline each and all questions), in an anonymized, cumulative data table. In anonymized digital and paper data records, we will collect behavioral data (time series reflecting the activity of body parts), EEG/EMG data. Data is acquired by an EEG/EMG/robotic computer system and custom-made computer programs.

(b) **storage of research information:** Anonymized data (random code identifier) will be encrypted and stored in a password protected computer in the laboratory of [name], and copied on password-protected digital media. Consents will be stored in a locked file cabinet in the laboratory of [name] and the key will be available in the principal investigator's office. Anonymized data will be accessed by the investigators listed on the IRB application. We will destroy the informed consents after a period of 4 years, but we will aim to preserve the anonymized data so that it can be further re-used by ourselves, collaborators and other scientists making request of them. We expect this study to be supported by NIH or NSF (grant submitted under a joint panel). NIH, as well as other agencies, have articulated a strong inclination for the preservation of taxpayer-funded scientific data (Collins & Tabak, *Nature*, 2014; Federer et al., *PLOS One* 2015). NSF has the following policy: *"Investigators are expected to share with other researchers, at no more than incremental cost and within a reasonable time, the primary data, samples, physical collections and other supporting materials created or gathered in the course of work under NSF grants. Grantees are expected to encourage and facilitate such sharing."*

(<https://www.nsf.gov/bfa/dias/policy/dmp.jsp>). It is also customary in our field that data is preserved for replications and confirmation studies, and several target publications for our research require that we accept requests for data sharing from other scientists.

10. Resources:

(a) **Resources/facilities at FAU:** Personnel involved in the data collection are Faculty at FAU, Drs [name] and [name], FAU students, and subjected to amendments of this IRB, to-be-hired postdoctoral fellows and research assistants. All have received a training for EEG recording and safety. Recordings will take place in the laboratory of [name], Engineering West.

(b) **Resources from other sites:** No research activities involving human subjects will be conducted at performance sites that are not owned or operated by FAU.

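### Section 4(e) compares about four to six outcomes over three feedback levels with no primary test, testing order or multiplicity rule

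*Combined protocol and SAP*

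**What the plan says.** Section 4(b) makes haptic feedback (full, partial, null) and object weight (heavy, medium, light) the main experimental factors. On outcomes it says that "behavioral performance scores (number of drop and breakage, speed) are recorded, as well as subjective self-report (perceived task difficulty".

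Section 4(e) then says: "We compare the neural (somatosensory neuromarkers) and behavioral characteristics (performance, subjective report) for each object weight and each feedback modality". It assigns Mann-Whitney tests to the subjective ratings, a multifactor ANOVA to drop/breakage success and to speed, and a cited method to the EEG. Its hypothesis is directional and forms a chain: better feedback gives stronger and earlier somatosensory activity, which in turn gives faster and better performance.

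The only error rate is in the sample-size paragraph of section 4(c): "standardized probability of 0.05 and statistical power of 0.8". No section names a primary outcome, a primary contrast, an order of testing or a multiplicity adjustment.

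**The concern.** With several outcomes, several contrasts and no ranking among them, a reader cannot tell in advance which result would confirm the hypothesis and which would count against it. Any single nominally significant comparison could be reported as support, and the chance of at least one such result under no effect exceeds the level of each test.

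The plan also gives no reading for mixed results. Its hypothesis predicts gains in both speed and quality. If drops fall but transport slows, or EEG activity is stronger but no earlier, the conclusion would be chosen after seeing the data.

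**Working it through.** **1. The plan's own figure.** Section 4(e) contains no error rate to reproduce. The nearby figure of seven subjects in section 4(c) cannot be reproduced either, because the effect size, metric, test and sidedness are not given. Back-solving from n = 7, level 0.05 and power 0.80 with a paired t-test (noncentral t, 6 df) gives a standardised difference of 1.27 if two-sided and 1.07 if one-sided. These are implied values, not stated ones. The calculation below does not use them.

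**2. Counting outcomes.** Five: drop/breakage success, speed, perceived difficulty, EEG strength, EEG timing. It is four if the EEG yields a single marker, and six if drops and breakages are analysed separately and both EEG features are kept.

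**3. One omnibus feedback test per outcome, independent outcomes.** Assume 0.05 per test. The chance of at least one false positive is 1 − 0.95^k:
- k = 4: 1 − 0.8145 = 18.5%
- k = 5: 1 − 0.7738 = 22.6%
- k = 6: 1 − 0.7351 = 26.5%

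**4. Correlated outcomes and pairwise contrasts.** I simulated a null within-subject design: normal data, three feedback levels, five outcomes, every test at 0.05, 20,000 runs per setting (simulation error about 0.3 to 0.4 percentage points). The omnibus test is a repeated-measures F; the pairwise tests are paired t-tests.

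| Subjects | Outcome correlation | One omnibus test each | Three pairwise tests each |
|---|---|---|---|
| 12 | 0 | 22.6% | 49.1% |
| 12 | 0.5 | 18.8% | 41.6% |
| 36 | 0 | 22.9% | 48.2% |
| 36 | 0.5 | 18.4% | 39.7% |

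The exact omnibus value under independence is 22.6%. Simulated values a little above it, up to 24% in smaller runs, are simulation error. With four outcomes the ranges are about 16–19% and 35–41%; with six, about 21–26% and 45–55%.

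**5. Which column applies.** A multifactor ANOVA gives one omnibus feedback test per outcome, so the third column fits success and speed as written. Mann-Whitney compares two samples, so covering three feedback levels for the ratings takes more than one test. No contrasts are specified for the EEG. The plan as written therefore lies between the two columns, at a point that cannot be fixed from the text. Separate comparisons within each weight would add to either column.

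Treating the 15 pairwise contrasts (5 × 3) as independent would give 1 − 0.95^15 = 53.7%. That overstates the rate, because the three contrasts within an outcome share data.

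**The case against.** **The 0.05 per test is not in the analysis plan.** Correct. It comes from the sample-size statement, so every rate above is conditional on it. That section 4(e) gives no level is part of the same gap.

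**The hypothesis is a chain, so support needs every link.** If the sponsor stated that all links must be significant, an at-least-one error rate would not apply. This is a fair reading, but the plan does not state it, and a single positive result remains open to being claimed.

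**Early work may be exploratory.** That would justify looser control. But the plan sets a directional hypothesis and cites a power calculation, and never calls itself exploratory.

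**The pairwise figures assume contrasts that the plan does not name for success and speed.** This stands, and the higher range must keep that condition.

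**A stronger reading of the sample size.** A reader might infer that the stated minimum of seven gives 80% power for only one of these tests and is therefore too small. The documents do not support this. The basis is "Based on a power analysis of preliminary data of grasp performance metrics with amputees and best estimates", with metrics in the plural, so seven could be the largest requirement among several. It is confined to behaviour: "a minimum of seven subjects will be required for adequately powered behavioral analysis". EEG has its own minimum ("EEG analysis, on its side, requires a minimum of 12 subjects per group"), and the planned size is larger: "our study aims for 3 x 12 subjects (control, amputees, limb absent".

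The opposite inference, that 12 per group is shown to be enough after adjustment, fails too. With five Bonferroni-adjusted two-sided tests (0.05/5 = 0.01) and n = 12, power is 87% at the implied effect of 1.27 but about 71% at 1.07. Both effects are back-solved, and neither need apply to every outcome.

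**Conclusion.** The point holds as a gap in error control and in the decision rule. With five outcomes at an assumed 0.05 each and outcome correlation from 0 to 0.5, the chance of at least one false-positive feedback result is about 18–23% with one omnibus test per outcome. It is about 40–49% only if all three pairwise contrasts are run for each outcome. Counting four or six outcomes moves these ranges but not the conclusion.

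No conclusion follows about the adequacy of seven subjects or of 12 per group, because the effect size, metric and test behind seven are not given. The plan should be changed on this point, but nothing here shows that the study is too small.

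**What to change.** In section 4(e), before any analysis:

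- Name one primary outcome and one primary feedback test at 0.05, two-sided if it is a contrast. Examples are the feedback main effect, or full versus null, on drop/breakage success. The choice is the sponsor's. Keep the partial, nerve-regeneration-dependent level in the analysis either way.
- Test EEG strength and EEG timing in a stated fixed order, each at 0.05 and only if the test before it succeeds.
- Apply Holm to speed, perceived difficulty and the by-weight contrasts. State whether this family is tested only after the earlier steps succeed, which controls the error rate overall, or regardless of them, which controls it within the family only.
- State that faster and better performance is claimed only if speed and success both support it.

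Leave the figure of seven as it is; this point gives no basis for replacing it.

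The cost is a few sentences in the plan. Secondary results become somewhat harder to call significant. Adopting the rule requires no added subjects, though power for the adjusted comparisons cannot be stated until the sponsor gives the effect sizes.

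### Mann-Whitney U-tests are assigned to difficulty ratings that the plan compares across within-subject conditions, so the pairing is ignored and the p-values are miscalibrated

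*Combined protocol and SAP*

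**What the plan says.** Section 4(e), Analysis Plan, states the comparison: "We compare the neural (somatosensory neuromarkers) and behavioral characteristics (performance, subjective report) for each object weight and each feedback modality". Later in the same section it names the test: "Nonparametric Mann-Whitney U-tests will be performed on the subjective evaluations". That sentence lists no contrasts.

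The design is described elsewhere:

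- Section 4(a): "The study includes a fractional factorial experimental design with repeated measurements".
- Section 4(b), Research Methods: haptic feedback is a factor "with three modalities: full, partial (nerve-regeneration dependent) and null". Object weight also has three levels. The subjective outcome is perceived task difficulty, with no scale given.
- Section 4(b), Procedures: "The task parameters are varied between trials (presence and quality of haptic feedback, weight of the visually-identical object").
- Section 4(b), Time commitment: "At the end of each experiment, subjects are offered continued participation over the consecutive days of the week". Further days are therefore optional.
- Section 4(c), Study Population: "our study aims for 3 x 12 subjects (control, amputees, limb absent"). These are the only independent groups in the study.

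For the ratings, the plan gives no paired or repeated-measures rank method, no reduction to one value per subject, and no adjustment for clustering. It does not say whether a rating is taken per trial, per block or per session.

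**The concern.** The Mann-Whitney test treats its two samples as coming from different people. Here the ratings under full, partial and null feedback, or under heavy, medium and light objects, come from the same people. The test leaves differences between people in the noise, whereas a paired method removes them.

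The test also handles only two levels at a time. Each three-level factor needs three pairwise tests, and no rule for that set is given.

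At stake is the finding on perceived difficulty. With one rating per subject per condition and positively correlated ratings, the test is too conservative and can miss a real difference between feedback modalities. With trial ratings pooled as if independent, the error can go either way. The plan does not say which case applies.

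**Working it through.** **No figure in the plan to reproduce.** The plan gives no operating characteristics for the ratings. Its minimum of seven subjects for the behavioural analysis comes without an effect size, SD or test, and nothing below depends on it.

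**Inputs from the plan.** Three levels per factor, varied within subject; 12 subjects per group, 3 x 12 = 36 in all. Section 4(c) uses 0.05 for the behavioural sample size; neither that level nor sidedness is stated for the ratings.

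**Assumed inputs.** Two-sided 0.05 test. A standard normal latent rating cut at -1.5, -0.9, -0.3, 0.3, 0.9 and 1.5 into 7 categories. Within-subject correlation ρ of 0.3, 0.5 or 0.7, with 0 as a reference.

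**Step 1: direction with one rating per condition.** The difference between two condition means has variance 2σ²(1-ρ)/n. A test that assumes independence uses 2σ²/n. Its statistic therefore has SD √(1-ρ) instead of 1, and the false-positive rate is about 2Φ(-1.96/√(1-ρ)):

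- ρ = 0.3: 2Φ(-1.96/0.837) = 2Φ(-2.34) = 1.9%
- ρ = 0.5: 2Φ(-1.96/0.707) = 2Φ(-2.77) = 0.6%
- ρ = 0.7: 2Φ(-1.96/0.548) = 2Φ(-3.58) = 0.03%

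This is a large-sample guide for means. The rank tests were simulated.

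**Step 2: simulation, one rating per condition** (4,000 runs per case, Monte Carlo SE at most 0.8 points; MW = Mann-Whitney, SR = signed-rank).

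| | ρ = 0.3 | ρ = 0.5 | ρ = 0.7 |
|---|---|---|---|
| n = 12, false positives, MW | 2.1% | 0.9% | 0.2% |
| n = 12, power, 0.8 SD shift, MW | 42% | 41% | 41% |
| n = 12, power, 0.8 SD shift, SR | 54% | 66% | 85% |
| n = 36, power, 0.5 SD shift, MW | 51% | 52% | 54% |
| n = 36, power, 0.5 SD shift, SR | 65% | 78% | 94% |

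The signed-rank false-positive rate at n = 12 is 4.5-4.7%. Relative loss of power is 1 - power(MW)/power(SR). At n = 12 it is 1 - 0.421/0.536 = 0.21, 1 - 0.414/0.6625 = 0.38 and 1 - 0.409/0.849 = 0.52. At n = 36 it is about 0.21, 0.33 and 0.42. At ρ = 0 nothing is lost (n = 12: 42% against 39%).

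Continuous normal ratings give nearly the same result: Mann-Whitney false positives at n = 12 are 2.1%, 0.9% and 0.2%, and at n = 36 they are 2.1%, 0.8% and 0.1%.

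**Step 3: trial ratings pooled as independent.** Let m be the ratings per condition and τ the SD, across subjects, of each subject's own condition difference (mean zero). The variance of a subject's mean difference is τ² + 2(1-ρ)/m. The test assumes about 2/m, ignoring the small addition of τ² to the total variance. The two are equal when τ² = 2ρ/m. At ρ = 0.5 that is τ = √(1/9) = 0.33 for m = 9 and τ = √(1/3) = 0.58 for m = 3. Below that value the test is conservative; above it, anti-conservative.

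Simulated false-positive rates at n = 12 over ρ = 0.3 to 0.7 (2,000 runs per case, SE at most 0.9 points):

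| Nine ratings per condition | τ = 0 | τ = 0.3 | τ = 0.5 | τ = 0.7 |
|---|---|---|---|---|
| MW, pooled | 0.4-1.9% | 3-6% | 10-13% | 19-21% |

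With three ratings per condition the range over the same τ values is 0.4-7.6%. The signed-rank test on subject means stays at 3.7-5.2% throughout.

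**Step 4: number of tests.** Three levels give 3 pairwise tests per factor, 6 for the two factors. Three independent tests at 0.05 would carry a family-wise rate of 1 - 0.95³ = 0.14. This is only a rough guide, because these tests are neither independent nor, as shown, at 5%.

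**The case against.** The best defence is that the Mann-Whitney sentence names no contrasts and may be meant for the three independent groups. The wording about each weight and each modality could be read as comparing groups within each condition. With one value per subject, Mann-Whitney between two groups is valid. That last point stands. But section 4(e) names no group contrast, and its hypothesis concerns trials with better or worse feedback, which is a within-subject comparison. If group contrasts were meant, the comparison the section does state has no test, and the text still needs correcting.

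A second objection is that the numbers rest on assumed correlations and shifts. This is true, and some cases come close to nominal: zero correlation with one rating per condition, or pooled ratings with moderate differences between subjects. It limits what can be said about size and direction. It does not make an independent-samples test suitable for paired data.

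A third is that ratings taken once per session could not be assigned to a feedback level or weight, so the remedy might need a change in data collection. That would equally defeat the plan's own stated comparison, which already requires ratings attributable to a condition.

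Finally, the outcome is secondary in importance. That is accepted and limits the weight of the point.

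**Conclusion.** The concern holds. As written, the plan assigns an independent two-sample test to ratings whose only stated comparison is within subjects.

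The direction of the error is not fixed by the documents, so it should be called miscalibration and not inflation. With one rating per condition and positive within-subject correlation, the cost is power: a relative loss of about 21-52% at n = 12 and 21-42% at n = 36, under the assumed shifts and correlations of 0.3 to 0.7. With pooled trial ratings, false-positive rates from 0.4% to 21% are possible under the assumptions used.

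Perceived difficulty is not named in the hypothesis and is not a basis for the sample size. The main EEG and performance conclusions do not depend on it. The point should be fixed, but it does not undermine the study.

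**What to change.** Revise section 4(e) as follows:

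1. State when ratings are taken, on what scale, and which contrasts are tested.
2. For feedback and weight comparisons, reduce to one summary rating per subject per condition. Average over the other factor only if its levels are balanced within each subject.
3. Where every subject has all compared conditions, use Friedman's test across the three levels, followed by Holm-adjusted Wilcoxon signed-rank tests (for feedback: full against null, full against partial, partial against null).
4. Where the fractional design or missed optional days leave empty cells, or feedback and weight are tested together, use an ordinal mixed model with a subject effect. Add a subject-by-condition effect if several ratings per condition are kept.
5. Keep Mann-Whitney only for comparisons between the independent groups (control, amputee, limb-absent), with one value per subject.

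The cost is a short paragraph. No extra subjects are needed, and no extra data provided that each rating is recorded against its condition, which the plan's stated comparison already requires. If ratings have already been collected on that basis, the same analysis can be applied to them and reported as a correction to the plan.
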